2.10.8 Early withdrawal and lost to follow-up

Study participants are free to withdraw from the investigation at any time without having to justify their reasons and without affecting their relationship with the investigator. An investigator may also withdraw a participant from the study at any time if it is determined to be in the participant's best interests.

A participant's future management will not be changed by a decision, voluntary or otherwise, to withdraw from the study. All reasonable efforts should be made to retain participants until completion of the clinical study. Reasons for termination or withdrawal include but are not limited to the following:

- Participant death
- Participant request
- Participant lost to follow-up. A participant is considered "lost to follow-up" after a minimum of 3 documented attempts to reach the participant. The last attempt must be by a traceable method (eg, read-receipt email, certified letter)
- Participant's participation terminated by the investigator
- Study terminated by the sponsor

For any participants with early withdrawal or termination, termination information will be recorded in the participant's records and the date of last contact with the participant noted in the study records.

2.10.9 End of study

Participants randomized to the control arm who do not crossover to active treatment are exited upon completion of their 90-day visit. For all other treated participants, the study is considered complete upon completion of the 365-day postprocedure visit.

If a participant has a ClariFix device inserted into their nose but does not undergo either an active or sham treatment, the participant will be contacted by phone approximately 30 days after the procedure to inquire about adverse events (AEs). If the participant has not experienced any device or procedure-related AEs, they can then be exited from the study. If the participant has an ongoing device or procedure-related AE, they will be followed until AE resolution or 90 days after the procedure, whichever comes first.

Study exit will be documented in the study records when the participant has completed their last required follow-up visit or at the time of withdrawal or lost to follow-up, if the participant discontinues the study prematurely.

2.11 Study assessments and data collection

Study data will be collected according to Good Clinical Practices. Source worksheets will be provided to the investigational sites for collection of study data. Data will be entered into the study database by investigational site staff using the Medrio EDC system. The data will be reviewed by Stryker ENT staff, or designee, and any queries will be submitted to the investigational center for clarification. Patient-reported outcome questionnaires may be entered into the EDC directly by study participants or entered by study staff from paper source documents.

The required study assessments for each specified interval are outlined in the **Sections 2.10.6** and **2.10.7**. See **Table 2** for an overview of the required study assessments at each follow-up visit. Each participant's follow-up schedule is based on the date of their study procedure.

2.11.1 Primary endpoint assessments

Reflective Total Nasal Symptom Score (rTNSS)

The reflective Total Nasal Symptom Score (rTNSS) is a validated patient-reported outcome (PRO) used to describe symptoms of rhinitis. ¹⁴ The assessment consists of 4 nasal symptom domains (runny nose [rhinorrhea], itchy nose, sneezing, and stuffiness [nasal congestion]). Each item is rated from 0 (absent) to 3 (severe). The 4 domains are added together to provide an overall score ranging from 0 to 12.

The primary efficacy endpoint is the comparison of active vs sham-control groups for the percent of responders at the 90-day follow-up. A responder is defined as a participant having a 30% or greater reduction in total rTNSS compared with baseline.

2.11.2 Secondary endpoint assessments

Reflective Total Nasal Symptom Score (rTNSS)

The rTNSS will be collected at screening, baseline, and all follow-up visits. The mean change from baseline in the rTNSS for both treatment groups will be evaluated and compared between treatment groups as a secondary endpoint at the 30-day and 90-day follow-up periods. Additionally, the mean change from baseline will be accessed at all follow-ups for all participants who received active treatment (randomized or crossover).

Rhinoconjunctivitis Quality of Life Questionnaire (RQLQ(S))

The RQLQ(S) is a validated PRO that measures functional impairments due to allergic or non-allergic rhinoconjunctivitis. ^{15,16} The assessment consists of 28 questions related to nose symptoms, eye symptoms, non-eye/nose symptoms, sleep problems, practical problems, activity limitations, and emotional function. Each item is scored from 0 (no impairment) to 6 (severely impaired). An overall score is calculated from the mean of the 28 item responses. Domain scores are the mean of the item scores within that domain. The RQLQ(S) differs from the initial RQLQ in that it standardizes the 3 activities reported for the duration of the study.

The RQLQ(S) will be completed at baseline and all follow-up visits. The mean change from baseline in the RQLQ(S) will be evaluated and compared between treatment groups as a secondary endpoint at the 30-day and 90-day follow-up periods. Additionally, the mean change from baseline will be accessed at all follow-ups for all participants who received active treatment (randomized or crossover).

EuroQOL (EQ-5D-5L)

The EQ-5D-5L is a validated, standardized questionnaire used to evaluate general health-related quality of life. ^{17,18} The questionnaire consists of 5 health dimensions (mobility, self-care, usual activities, pain/discomfort, and anxiety/depression) and a visual analog scale (VAS) to indicate overall health on a scale of 0 to 100. Each health dimension has 5 possible responses: no problems, slight problems, moderate problems, severe problems, or extreme problems. The questionnaire is designed to be self-completed by the participant.

The EQ-5D-5L will be completed at baseline and all follow-up visits. The mean change from baseline in the EQ-5D-5L will be evaluated and compared between treatment groups as a secondary endpoint at the 30-day and 90-day follow-up periods. Additionally, the mean change from baseline will be accessed at all follow-ups for all participants who received active treatment (randomized or crossover).

Satisfaction questionnaire

The satisfaction questionnaire consists of 3 questions that the participant answers at each follow-up visit. The questions indicate whether the participant is satisfied with the procedure outcome, whether the participant would undergo the procedure again for similar results, and whether the participant would recommend the procedure to family or friends with a similar condition. For each item the participant indicates agreement/disagreement with each statement.

Serious device- or procedure-related adverse events (SAEs)

The rate of serious device- or procedure-related adverse events (SAEs) will be compared between treatment groups through the 90-day follow-up visit (**Section 6**). The parameter of interest is the percent of participants who experience 1 or more device- and/or procedure-related SAEs from the time of the index procedure through the 90-day follow-up.

2.11.3 Additional assessments

Blinding questionnaire

The blinding questionnaire is intended to assess the adequacy of participant blinding. Participants are asked to indicate which study arm (active or sham) they believe they were assigned to, the reasons for their belief, and other questions to assess the overall treatment experience. The blinding questionnaire will be completed immediately post procedure and at follow-up visits through 90 days from the initial randomized treatment only (active or sham).

Nasal Obstruction Symptom Evaluation (NOSE) questionnaire

The NOSE scale is a standardized, validated PRO that evaluates the patient's perception of their ability to breathe through their nose. ¹⁹ Patient's rate to 5 items (nasal congestion or stuffiness, nasal blockage or obstruction, trouble breathing through the nose, trouble sleeping, and unable to get enough air through the nose during exercise or exertion) on a scale of 0 (not a problem) to 4 (severe problem). The sum of the items is multiplied by 5 to provide an overall score with a possible range of 0 to 100, with higher scores indicating worse symptoms. This is an exploratory outcome measure.

3 Risk/Benefit Analysis

3.1 Benefits

Participation in this study is voluntary. Participants with rhinitis may experience an improvement in their symptoms.

3.2 Potential risks

Study participants will be informed of all known potential side effects and complications associated with study treatment and study assessments before consenting for the study. The risks associated with participating in the study are the same as those that the participant would have if treated with nasal cryotherapy outside of the study.

While endoscopic rhinoscopy is generally known to be safe, anticipated risks may include, but are not limited to:

- Temporary pain, discomfort or irritation
- Bleeding
- Cerebrospinal fluid (CSF) leak

Similarly, while generally known to be safe, submucosal placement of a needle and delivery of local anesthesia may be additionally associated with the following risks, not limited to:

- Minor bleeding
- Pain with injection
- Facial numbness or tingling
- Sedation
- Tachycardia, nervousness, anxiety
- Lightheadedness, dizziness, confusion
- Muscular twitching, tremors
- Infection
- Allergic reaction
- Lidocaine or tetracaine toxicity with overdose

- Visual disturbance
- Vomiting
- Headache
- Tinnitus
- Seizures
- Hypotension, bradycardia
- Unconsciousness
- Respiratory arrest
- Cardiac arrest

In addition, the specific nature of cryosurgery using the ClariFix device results in a known potential for adverse events related to the cold application, including but not limited to:

- Bleeding
- Crusting and/or tissue sloughing
- Swelling
- Pain/discomfort and/or facial pain
- Increase in nasal congestion
- Intranasal scarring/nasal obstruction
- Sensory alterations (numbness, tingling) in the face/mouth

- Headache
- Dry nose
- Ear blockage
- Septal perforation
- Vasovagal reaction
- Infection
- Dry eyes, optical changes or orbital damage

Also refer to the manufacturer's Instructions for Use (IFU) provided with the device.

There is also a possible risk of a loss of confidentiality. The sponsor will take all reasonable efforts to prevent the release of confidential participant information in accordance with the local and national privacy laws.

3.3 Risk mitigation

The protocol has been developed to minimize the risks for the participant in a number of ways. Sample size was calculated to expose the smallest number of participants while still being able to adequately test the study hypothesis. The procedure will be performed by practicing otolaryngologists experienced in transnasal procedures and trained on the use of the ClariFix device. Investigators are expected to comply with the manufacturer's IFU for the ClariFix device. The participant selection criteria have been designed to minimize risk by excluding patients who have comorbidities or conditions that may put the patient at higher risk for cryotherapy. Specifically, patients with known allergies to local anesthetic agents are excluded from participation in the study. Women of childbearing potential will be required to take a urine pregnancy test before the procedure to allow for appropriate selection of procedure anesthesia medications that are safe to use during pregnancy. Concomitant procedures that could increase risk and confound study results are not permitted during the study. Finally, the participants will be closely monitored by frequent follow-up visits during the study.

4 Device Information

4.1 Investigational device description

The study device is the ClariFix[®] Cryotherapy device (ClariFix). The device is currently a Class I, 510(k)-cleared, commercially available device for chronic rhinitis. Use in this study is on-label with the cleared indications for use.

The ClariFix device is a handheld, single patient-use, disposable cryosurgical device used for the destruction of tissue during surgical procedures. The device consists of a handle attached to a

cannula with a cryoprobe at the distal end. The ClariFix device is provided sterile to the user. See the IFU packaged with the device for further information.

4.2 Investigational device management

ClariFix devices will be provided to the investigational centers specifically labeled "for study use only". Active and sham devices will be identical. The cryogen cannister will not be inserted in the device for the sham procedures.

The sponsor will monitor use of the study devices by the following activities:

- Shipping or hand-carrying devices only to approved investigators who are participating in the study
- Maintaining records of shipment and distribution of the devices
- Maintaining records of devices used on participants and returned devices

4.3 Device malfunctions

A device malfunction is defined as a failure of a device to meet its performance specifications or otherwise to perform as intended. A malfunction may be a result of any of the following: failure, malfunction, improper or inadequate design, manufacturing, labeling, or user error.

All device malfunctions must be reported to the sponsor. All attempts should be made to return malfunctioning devices to Stryker ENT for evaluation. Contact the clinical monitor for instructions on used device preparation and return procedures.

5 Monitoring Procedures

Stryker ENT personnel or qualified designees will monitor the clinical study in a manner consistent with 21 CFR 812, Subpart C, Responsibilities of Sponsor. Contact information will be provided separately.

5.1 Investigators

The clinical monitors will ensure investigators are selected based on their qualifications and ability to fulfill the investigator responsibilities as outlined in **Section 9.6**.

The Lead Investigator for the study is [name] of the Icahn School of Medicine, Mount Sinai, New York, NY.

5.2 Investigational center monitoring

A risk-based approach to monitoring of the study will be utilized and outlined in a Clinical Monitoring Plan. Monitoring visits to the investigational centers will be conducted at a frequency sufficient to ensure that all aspects of the current approved protocol and any amendment(s) are followed. Source documents will be reviewed for verification with data in the eCRFs and all regulatory documents will be checked for accuracy including but not limited to IRB approvals,

study-related correspondence, and participant informed consent. The investigator and/or investigational center staff must be available to meet with the sponsor during monitoring visits.

Upon reasonable notice, the investigator and institution agree to provide the sponsor representatives or designees and applicable regulatory authorities with direct access to source documents relevant to the study for sponsor quality assurance audits or inspections by the regulatory authorities.

6 Adverse Event Definitions and Reporting

6.1 Adverse events and serious adverse events

An adverse event (AE) is any undesirable clinical occurrence experienced by the participant during the follow-up period regardless of the event's relationship to either the study device or procedure. An underlying disease that was present at the time of enrollment is not an AE; however, any increase in the severity of an underlying disease is an AE.

A serious adverse event (SAE) is an event that results in any of the following:

- Death
- Life-threatening
- Hospitalization or prolongation of an existing hospitalization
- Invasive surgical intervention to correct or prevent further injury
- Persistent or significant disability or incapacity
- An important medical event

An important medical event that may not meet one of the above definitions might be considered as an SAE if it jeopardizes the health of the participant or requires surgical intervention to prevent one of the outcomes listed in the above definition.

An elective hospitalization/intervention that was planned before the participant enrolled in the study is not considered an SAE as defined above.

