2.8.2 Exclusion criteria

Study participants MUST NOT meet any of the following criteria:

- 1. Have clinically significant anatomic obstructions that, in the investigator's opinion, limit access to the posterior nose, including but not limited to severe septal deviation or perforation, nasal polyps, and/or sinonasal tumor.
- 2. Have had previous sinus or nasal surgery within 6 months of study enrollment.
- 3. Have previously undergone cryotherapy or other surgical interventions for rhinitis.
- 4. Have an active nasal or sinus infection.
- 5. Have rhinitis symptoms that are primarily due to seasonal allergies.
- 6. Have plans to (or otherwise anticipates the need to) undergo an ENT procedure concurrently or within 3 months after the study procedure.
- 7. Is on prescribed anticoagulants (eg, warfarin, Plavix) or 325 mg aspirin that cannot be discontinued before the procedure (81 mg aspirin and herbal supplements are acceptable).
- 8. Be unable to discontinue ipratropium bromide (IB) at least 14 days before baseline and through the 90-day follow-up visit.
- 9. Have a history of chronic epistaxis or experienced a significant epistaxis event (defined as epistaxis event requiring medical intervention) in the past 3 months.
- 10. Have a history of rhinitis medicamentosa.
- 11. Have had previous head and/or neck irradiation.
- 12. Have an allergy or intolerance to local anesthetic agents.
- 13. Have cryoglobulinemia, paroxysmal cold hemoglobinuria, cold urticaria, Raynaud's disease, and/or open and/or infected wounds at or near the target tissue.
- 14. Have a neurological, medical, psychiatric condition, or social circumstance that would potentially increase risk, interfere with study participation, or confound interpretation of study data
- 15. Be participating in another clinical research study.

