2.10.5 Procedure (Active and Sham)

Pregnancy testing

Before the procedure, urine pregnancy tests are required for all women of childbearing potential. In the case of pregnancy, use medical judgement to select appropriate procedural anesthesia medications (eg, low doses of epinephrine and lidocaine) that are safe for use during pregnancy.

Procedure anesthesia

The local anesthesia regimen for the procedure for both active and sham treatments will be performed according to the physician's usual practice. Information regarding the anesthesia regimen will be documented in the study records.

Study procedure

Below is a high-level description of the procedure for both the active and sham procedures. Detailed instructions on the preparation, usage, and storage of the ClariFix device is available in the instructions for use (packaged with the device). To maintain the participant blind during the procedure, the sham devices will be identical to the active devices except the cryogen cannister will not be inserted into the device.

- 1) Review and update concomitant medications.
- 2) Perform quantitative endoscopic rhinoscopy before administration of nasal decongestant to evaluate nasal congestion.
- 3) Administer decongestant. If the participant is a woman of childbearing potential, use medical judgement to select a decongestant (eg, oxymetazoline) that is safe to use during pregnancy.
- 4) Perform quantitative endoscopic rhinoscopy to assess degree/extent of rhinorrhea and postdecongestant nasal congestion, and plan target treatment placement at the middle meatus.
- 5) Administer local anesthesia to both sides of the nasal cavity.
- 6) Have the participant put on the blindfold.
- 7) Prepare the ClariFix device according to the IFU (for sham treatment, do not insert the cryogen cannister).
- 8) Place the cryoprobe in firm contact with the targeted middle meatus tissue under visual guidance.

- 9) For active treatment: initiate the flow of cryogen for a total of 30 seconds and, using endoscopic visualization, ensure the cryoprobe is functioning.

 For sham treatment: turn on the device and leave the cryoprobe in contact with tissue for the 30 seconds, tissue will not freeze with the sham treatment. Use a separate device held near the participant to provide the sound of gas release from the cannister.

 For both treatments, during this time, instruct the participant breathe in and out through their mouth.

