6.2 Assessing, recording, and reporting of adverse events

For the purposes of this study, all serious adverse events (regardless of relationship) must be reported. Only nonserious adverse events that are related to the device, procedure, or the participant's ENT condition(s) should be reported. Nonserious adverse events that are not related to the device, procedure, or ENT conditions should not be reported.

An adverse event may be volunteered spontaneously by the participant or discovered by the investigator or study staff upon questioning or physical examination of the participant. The following information should be reported for all reportable adverse events and updated as needed until the event resolves:

- Adverse event (diagnosis associated with the main complaints or symptoms)
- Date the adverse event occurred
- Date the investigator (or staff) became aware of the adverse event

- Adverse event details (main complaints or symptoms)
- Relationship to study device
- Relationship to the study procedure
- Seriousness of the adverse event.
- Interventions undertaken
- Status of the adverse event (ongoing, resolved, unresolved but stable, death)
- Date of event resolution, if applicable

Source documents (eg, procedural notes, treatment notes, clinical summary) may be required as supporting documentation for an adverse event.

Any serious device- or procedure-related adverse events should be reported to the sponsor as soon as possible (preferably within 24 hours) after the investigator or clinic staff become aware of the event. Initial report of the event can be by email and/or telephone call to a sponsor representative.

During the study, **all** participant deaths must be reported to the sponsor within **24 hours** of the investigator's (or designated staff's) knowledge of the death. Deaths should be reported as the reason for study exit and the cause of the death should be reported as an adverse event. A copy of death records, medical records for the event(s) that led to the participant's death, death certificate (if available), and an autopsy report (if performed) should be deidentified and sent to the sponsor as soon as they become available for any death deemed related to the device and/or procedure.

7 Protocol Deviations

Investigators are required to adhere to the study protocol, applicable national or local laws and regulations, and any conditions required by the applicable IRB or regulatory authority.

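### Treatment during pregnancy is allowed, but the adverse event rules have no fetal or birth outcome and no pregnancy reporting, so some harm to a pregnancy could go unrecorded

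*Combined protocol and SAP*

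**What the plan says.** **Treatment in pregnancy.** None of the 15 exclusion criteria in section 2.8.2 names pregnancy. The nearest is criterion 14, a general clause left to judgement: "Have a neurological, medical, psychiatric condition, or social circumstance that would potentially increase risk". Section 3.3 gives the purpose of the test: "Women of childbearing potential will be required to take a urine pregnancy test before the procedure to allow for appropriate selection of procedure anesthesia medications". Section 2.10.5 covers a positive result: "In the case of pregnancy, use medical judgement to select appropriate procedural anesthesia medications". Neither section says that a positive test stops the procedure.

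**Definitions.** Section 6.1 defines an adverse event as "any undesirable clinical occurrence experienced by the participant during the follow-up period". Its criteria for a serious event are death, threat to life, hospitalization, invasive surgical intervention, disability and important medical event. The last is discretionary and is tied to the participant's own health or to surgery that prevents one of the other outcomes. No criterion refers to a fetus or newborn.

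**Reporting.** Section 6.2 requires all serious events to be reported whatever their cause, and nonserious events if they are related to the device, the procedure or an ENT condition. For the rest it says: "Nonserious adverse events that are not related to the device, procedure, or ENT conditions should not be reported".

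**Follow-up.** Section 2.10.9 says: "Participants randomized to the control arm who do not crossover to active treatment are exited upon completion of their 90-day visit". Everyone who receives cryotherapy, whether randomized or by crossover, is scheduled to day 365.

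No section asks for a pregnancy to be notified or its outcome recorded.

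**The concern.** The protocol foresees that a participant known to be pregnant may receive a decongestant, a local anesthetic and, in the active arm, cryotherapy. Its safety rules were written as if pregnancy could not occur. A site that follows sections 6.1 and 6.2 to the letter would have no basis for recording some pregnancy outcomes and would be told not to report others.

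At stake is the completeness of the safety record for a few participants. If a pregnancy went badly in a way that the definitions do not cover, the sponsor and the IRB might not learn of it through the study. Any information that did arrive would also differ by arm, because scheduled follow-up is 90 days for sham participants who do not cross over and 365 days for everyone given cryotherapy.

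**Working it through.** The plan gives no figure on this point to reproduce. The check has three parts: possible outcomes set against the rules, the time available to observe them, and a rough count.

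**1. Outcomes against the rules in 6.1 and 6.2**

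| Outcome in a pregnant participant | Reportable under the text? |
|---|---|
| Loss or complication with hospital admission, threat to life or invasive surgery | Yes, as a serious event, whatever its cause |
| Nonserious loss judged related to device or procedure | Yes |
| Loss without admission or invasive surgery, classed as an important medical event | Yes, but the classification is discretionary |
| The same loss, judged nonserious and unrelated | No; barred by 6.2 |
| Congenital anomaly or other fetal or newborn harm that meets no maternal criterion | No; outside the adverse event definition |
| Any outcome after study exit | No; outside the follow-up period |

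The relatedness judgement in the fourth row is made at sites that are not blinded: under section 2.10.4 only the participant is.

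**2. Follow-up time**

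Assumption, not in the documents: a term pregnancy lasts 280 days. From Table 2, the 90-day visit falls on days 76 to 104 and the 365-day visit on days 344 to 386.

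Gestation needed at the procedure for a term delivery before exit = (280 − exit day) / 7:

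- exit on day 76: (280 − 76)/7 = 29.1 weeks
- exit on day 90: (280 − 90)/7 = 27.1 weeks
- exit on day 104: (280 − 104)/7 = 25.1 weeks

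So for a sham participant who does not cross over, a pregnancy of less than about 25 to 29 weeks at the procedure would reach term after exit. For a participant given cryotherapy, even the earliest 365-day visit (day 344) is later than day 280, so a pregnancy present at the procedure would reach term within follow-up. A pregnancy dated from after about day 365 − 280 = 85 would not.

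**3. Expected number**

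Assumptions, not in the documents: 30% to 50% of the 128 participants are women of childbearing potential, and 0.5% to 2% of those test positive on day 0.

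Expected exposed pregnancies = 128 × share × positive rate:

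- low: 128 × 0.30 × 0.005 = 0.19
- high: 128 × 0.50 × 0.02 = 1.28

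Chance of at least one = 1 − (1 − share × rate)^128:

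- low: 1 − 0.9985^128 = 0.17
- high: 1 − 0.99^128 = 0.72

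In the sham arm (128/2 = 64) the expected number is 0.10 to 0.64, before those who cross over are removed. Pregnancies that begin during follow-up are not in these counts.

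**The case against.** A reader might infer that harm to a pregnancy would go unrecorded altogether. The text does not support that. A pregnancy loss is itself an occurrence in the participant. The criterion "Hospitalization or prolongation of an existing hospitalization", threat to life and invasive surgical intervention would each make it a serious event that must be reported even if unrelated. The important medical event clause is a further route, and nonserious related events are reportable.

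A reader might also infer that the gap distorts the secondary endpoint on serious device- or procedure-related events. That endpoint counts only related serious events (section 2.11.2), so a loss judged unrelated would not enter it under any reporting rule. Nor does the gap cost the trial a finding on safety in pregnancy. No objective seeks one, and about one case could not support it even with perfect recording.

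Other points on this side also carry weight. Criterion 14 lets an investigator exclude a pregnant candidate, so the protocol permits such treatment and does not set out to give it. The early exit applies to sham participants who receive no cryotherapy. The device is described as cleared and used on-label (section 4.1). The pregnancy test is a scheduled item in Table 2, so its result may well be captured. The case report forms and consent pages are not available here, and section 10.2 lets an IRB add its own reporting requirements. Finally, the assumed range is too wide to carry much weight.

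These points narrow the gap but do not close it. An unseen form or a local IRB rule is no substitute for a reporting rule in the protocol, and none of these points reaches a congenital anomaly or an early loss that section 6.2 tells sites to leave out.

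**Conclusion.** The point holds in a limited form: harm to a pregnancy could, not would, go unrecorded, and only in three cases:

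- (a) fetal or newborn harm that meets no maternal serious criterion, such as a congenital anomaly;
- (b) an early loss managed without hospitalization or invasive surgery, not classed as an important medical event, and judged nonserious and unrelated by unblinded site staff;
- (c) outcomes after study exit, mainly in sham participants who do not cross over.

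Cases (a) and (b) follow from the wording of sections 6.1 and 6.2 alone. Case (c) also rests on the assumed 280-day term. The size is small: roughly 0 to 1 exposed pregnancy at the day-0 test, on assumed rates. No efficacy endpoint, sample size or trial conclusion changes. The correction is still worth making, because the protocol itself provides for treatment after a positive test and the recording rule has to exist before the first case. Whether pregnant participants should be treated is a clinical question on which no view is taken.

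**What to change.** - **Section 6.1:** add fetal death or loss, and congenital anomaly or birth defect, to the serious criteria. State that these count although they occur in the fetus or newborn, and although they may come to light after the participant's last visit.
- **Section 6.2:** require every pregnancy found at the day-0 or crossover test, or learned of during follow-up, to be reported whatever its relationship to device or procedure. Record its outcome by one contact after the expected delivery date, including for sham participants who have already exited.

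The cost is one case report form and one contact per pregnancy. Contact after exit and collection of newborn outcomes would probably also need a consent-form amendment, with sponsor and IRB approval under sections 9.3 and 9.5. Visits and procedures for other participants do not change.
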